## **Materials and methods**

### ***Context, design, and randomization***

[figure not shown]
This study will be carried out in a northeast region of Spain [details masked for review process]. PE is mandatory for every secondary school student in Spain. Each student receives two 50-minute coeducational PE lessons per week. Spanish Secondary PE teachers are expected to teach between 18 and 21 hours per week. Typically, the annual teaching plan of PE teachers includes approximately six to eight distinct teaching units per year. These units encompass various content types such as individual, cooperative, and interactive sports and games, as well as body expression, health-related fitness, and outdoor activities, all of which are outlined in the PE curriculum. The academic year lasts from September to June, divided into three terms, each separated by a holiday period (i.e., Christmas and Easter).

A randomized controlled trial design with a mixed-method approach will be carried out. PE teachers agreeing to participate in the trial will be randomly assigned to either the experimental or the control group. Randomization will be conducted using the digital tool available at <https://echaloasuerte.com/>. To prevent contamination of the experimental condition, schools will only participate in one group (i.e., experimental or control). Subsequently, at least two groups of students from each PE teacher will be randomly selected.

This study will comprise two phases: 1) a teacher-training phase and 2) an implementation phase with students. It should be noted that the training program will continue with some individual and group sessions during the implementation phase. Since teachers' and students' perceptions of (de)motivating teaching styles and approaches and other study variables require several months for greater accuracy in their perceptions, the

training program will not start until the second term of the academic year (for more details see Figure 1).

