### ***Participants and recruitment***

At least 16 secondary PE teachers, eight in the experimental group and eight in the control group, along with their respective students, will be expected to participate in this study. The maximum number of participating teachers will be capped at 20, due to the limited human resources of the research team. PE teachers will select at least two classroom groups comprising at least 14 students each to invite to participate in this study. Eligible students will be those aged 12 to 17 years in secondary schools. Participation will be voluntary and anonymous.

Various social media platforms (i.e., Instagram, Twitter, and WhatsApp) and other communication methods (i.e., email) will be used for teachers' recruitment. An informative poster will be launched, detailing the target sample, content, aims, and training program dates. This poster will also include two links (QR code): one with a document providing further information and another to registration through a brief Google Forms questionnaire. Regarding the additional information document, it is important to note that it will detail a more comprehensive overview of the objectives, the different phases of the program, inclusion criteria, the requirements that each teacher must accept to participate, and the

teaching skills that will be developed during the training program. Teachers with further inquiries can contact the research team via email or phone. The registration period will last approximately 21 days.

Once the interested PE teachers have registered, various inclusion criteria will be considered for the final selection: 1) Being an in-service PE secondary school teacher for the entire academic year; 2) Attending 100% of the training program sessions; 3) Fill in a short questionnaire at the end of each session of the training program, as well as fulfilling questionnaires of the study variables three times; 4) Allowing the recording of two PE lessons; 5) Participating in two focus groups, one at the end of the training program and one at the end of the study, and 6) Not participating in other training sessions related to PE instruction during the program. Moreover, the inclusion criteria for students will be: 1) Authorization from parents or legal guardians; 2) Completion of questionnaires of the study variables three times; 3) Regular participation in PE lessons.

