## ***Measures***

### ***Questionnaires***

The following PE teachers' variables will be measured using Google Forms before the training program (T1), as well as during (T2) and at the end of the implementation of the intervention with their students (T3) (see Figure 1):

**Socio-demographic variables.** Age, gender, teaching experience, type of school (public or private), and school location (rural or urban) will be self-reported by teachers.

**(De)motivating teaching styles and approaches towards students.** To assess self-reported (de)motivating teaching styles toward students, the Spanish version of the SIS in Physical Education (SIS-PE; (Burgueño, Abós, et al., 2024) will be used. The SIS-PE comprises 12 typical teaching situations consisting of four items each (i.e., 48 items). Autonomy-supportive items are categorised into participative (four items) and attuning (eight

items) approaches. Structure items are operationalised into guiding (seven items) and clarifying (five items) approaches. Control items are divided into demanding (seven items) and domineering (five items) approaches. Chaos items are operationalised into abandoning (eight items) and awaiting (four items) approaches. For instance, this situation “At the start of class...” is followed by four items: you can explore students’ prior knowledge of the topic (attuning), set up a class clearly and straightforwardly (clarifying), demand application of what’s taught (demanding), or just begin and let the class evolve (awaiting)”. It should be noted that, since teachers’ perceptions of their (de)motivating teaching styles could be different according to the classroom group, teachers will have to answer the questionnaire taking into account the groups of students selected for the study. Teachers’ responses will be assessed using a 7-point Likert scale ranging from 1 (“Does not describe me at all”) to 7 (“Describes me perfectly”).

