**Quality of the training program.** Consistent with previous studies (Aelterman et al., 2013; Cheon & Reeve, 2015; Slingerland et al., 2017), a short paper-and-pencil questionnaire will also be measured immediately after each session of the training program carried out to gain insight into their content. Questions will be related to: (1) Interaction, (2) innovation, (3) interest, (4) intelligibility, (5) essentiality, (6) practical usefulness, (7) feasibility of the motivating strategies, (8) intention to implement the motivating strategies, (9) the extent to which one would recommend the training to others, (10) perceived changes in their (de)motivating styles, and (11) overall satisfaction. This questionnaire will be rated on a 5-point Likert scale from 1 (totally disagree) to 5 (totally agree), except for the last question, in

which teachers will rate the overall satisfaction on a scale from 1 to 10. Lastly, in an open-ended question, teachers will be able to detail the strengths and areas for improvement in each of the sessions to make slight adjustments to the training program in their future implementation.

Like their teachers, students will fill out the following questionnaires before the training program (T1), as well as during (T2) and at the end of the implementation of the intervention by the PE teachers (T3) (See Figure 1). Depending on the protocol of each school, these questionnaires will be completed in paper-and-pencil format or using Google Forms in a quiet classroom environment. The PE teacher will not be present when their students complete the questionnaires to avoid bias in the responses. In this sense, a member of the research will help the students with any doubts that may exist.

**Socio-demographic variables.** Age, gender, and school grade level will be self-reported by students.

**(De)motivating teaching styles and approaches.** To assess students' perceptions of (de)motivating teaching approaches of their PE teachers, the Spanish version of students of the Situations-in-School Questionnaire in Physical Education (SIS-PE; (Burgueño, Abós, et al., 2024) will be used. The only change in the instrument compared to the teachers' instrument is the structure of the sentences, as they are written from the students' perspective (e.g., "Your teacher invites you to suggest a set of norms or rules").

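### Classes are selected only after teachers are randomised, so parental authorisation and the T1 baselines follow allocation with no stated concealment, and enrolment and self-rated baselines can depend on arm

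*Protocol*

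**What the plan says.** **Order of allocation and class selection.** Context, design, and randomization states: "PE teachers agreeing to participate in the trial will be randomly assigned to either the experimental or the control group". Class selection comes next: "Subsequently, at least two groups of students from each PE teacher will be randomly selected".

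**Student entry.** Under Participants and recruitment, "the inclusion criteria for students will be: 1) Authorization from parents or legal guardians; 2) Completion of questionnaires of the study variables three times".

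**Timing of T1.** The student baseline is fixed by the words "students will fill out the following questionnaires before the training program (T1" and the teacher baseline by "variables will be measured using Google Forms before the training program (T1". Both are placed relative to the training, and neither relative to randomisation.

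**Link between the teacher baseline and the selected classes.** For the teaching-style questionnaire (SIS-PE), "teachers will have to answer the questionnaire taking into account the groups of students selected for the study".

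**Analysis.** The Analysis plan uses a 3 x 2 (time x condition) repeated measures MANCOVA with T1 as one level of time, followed by between-group and within-group tests. Student covariates are age, gender and grade level.

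**The concern.** In a trial that randomises teachers, students who enrol after allocation are protected by the randomisation only if enrolment cannot depend on the arm. The same holds for baselines collected after allocation. The stated order gives neither protection. A random draw of classes protects which class is chosen. It does not protect which families authorise or how T1 is answered.

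The protocol itself gives T1 a different use in the two arms. In the experimental arm, the pre-test values feed an individual report on the teaching profile during the implementation phase. Control teachers receive their report and training only after the last measurement. Lesson recordings are described for experimental teachers only, so no observed baseline exists against which a shifted self-report could be seen.

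At stake are the teacher time x condition effects, which use a self-rated T1 directly, and the between-group comparisons in students, which rely on the two enrolled samples being alike.

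**Working it through.** The plan gives no figure for this point. The anticipated effect size of 0.5 (Sample size calculation) serves only as a yardstick.

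**Step 1: the order of events.**
1. Teachers agree and are randomised (Context, design, and randomization).
2. Classes are selected afterwards (same section).
3. Families can be invited, and can authorise, only once the class is known. Authorisation therefore follows step 2.
4. Enrolled students complete T1, which follows step 3.
5. Teachers answer the SIS-PE about the selected classes, so that T1 also follows step 2.
6. The other teacher scales (needs at work, job satisfaction, exhaustion, performance) are not class-specific. They follow allocation only if given at the same sitting.

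**Step 2: a shift in teacher self-report at T1.** The contrast of interest is

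C = (T3 − T1 in experimental) − (T3 − T1 in control).

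If knowledge of the arm adds b_E and b_C to the T1 ratings alone, the observed contrast is C − (b_E − b_C), so the shift passes through one for one. If experimental teachers rate themselves lower, the effect is inflated. If they rate themselves higher, it is masked. To show scale only, an assumed difference of 0.2 SD moves C by 0.2 SD, or 0.2/0.5 = 40% of the yardstick. The documents support no particular value.

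**Step 3: differential enrolment of students.** Assume that the most willing share p of families authorises and that willingness correlates r with the outcome. The mean of the enrolled students then shifts by r·φ(z_p)/p, where z_p is the standard normal quantile of p.

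- p = 0.6: φ(z_p)/p = 0.644
- p = 0.7: 0.497
- p = 0.8: 0.350

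The difference between arms is D = 0.644 − 0.350 = 0.294 for 80% against 60%, and D = 0.497 − 0.350 = 0.147 for 80% against 70%. Multiplying by r gives the baseline difference in SD:

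| Authorisation | r = 0.1 | r = 0.3 | r = 0.5 |
|---|---|---|---|
| 80% v 60% | 0.029 | 0.088 | 0.147 |
| 80% v 70% | 0.015 | 0.044 | 0.073 |

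With positive r, the arm with the lower rate has the higher mean. Rates and correlations are assumptions; the protocol gives none.

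**Step 4: which analysis this reaches.** Let willingness correlate r1 with the outcome at T1 and r3 at T3. The between-arm difference at T3 is shifted by r3·D, and the change contrast by (r3 − r1)·D. If r1 = r3, the change contrast is not shifted at all. With r1 = 0.3, r3 = 0.2 and D = 0.294, the change contrast moves by 0.1 × 0.294 = 0.029 SD, while the T3 comparison moves by 0.2 × 0.294 = 0.059 SD.

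**The case against.** The strongest objection concerns the students. The same students are measured at T1, T2 and T3, so a stable difference in who enrols cancels in the time x condition contrast. This stands. A reader might take the 0.015 to 0.15 SD as bias in that effect, but step 4 shows that it is not. It applies to the between-group comparisons, and reaches time x condition only where willingness or baseline level predicts change.

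A reader might also infer that everyone knows the arm at T1 and that nobody is blinded. The text does not say so. It gives no date for telling teachers their arm, and the timeline figure is not available here. What it supports is that these steps follow allocation and that no concealment is stated.

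It is equally fair that the protocol does not say who collects the authorisations, or that families are told the arm. Teachers are kept out of the room when students answer, which limits their direct influence on student T1. This weakens the case for a shifted student T1 but leaves teacher self-report untouched.

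Finally, Participants and recruitment says "PE teachers will select at least two classroom groups comprising at least 14 students each to invite to participate in this study", with no order relative to the draw. That conflicts with a random selection of classes and needs reconciling in its own right. It does not undo the only order that the protocol states, and teachers choosing classes after allocation would add a second route to selection.

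**Conclusion.** The point holds as a weakness in a stated order, not as a missing detail. Class selection, authorisation, student T1 and the teacher SIS-PE T1 follow allocation, and no concealment is stated. Enrolment and self-rated baselines can therefore depend on arm; the documents do not show that they will.

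The main risk is the teacher self-report at T1, which passes one for one into the T1 to T3 contrast by an unknown amount and in an unknown direction. Differential enrolment is secondary: about 0.015 to 0.15 SD at baseline under the assumed rates and correlations, relevant mainly to the between-group comparisons. Age, gender and grade level do not measure willingness, so those covariates cannot be relied on to remove it. Adjusting for T1 would not repair a T1 that had itself been altered by knowledge of the arm.

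**What to change.** Rewrite the sequence in Context, design, and randomization as follows:

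1. Teachers register and are enrolled.
2. The two or more classes per teacher are fixed.
3. Parental authorisations are collected and the student list is closed.
4. Teachers and students complete T1.
5. Only then is the draw made and the arm disclosed, before training starts in the second term.

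State that no student is added after the draw. Align Participants and recruitment with this order.

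**Cost.** No extra data, staff or sample is needed, and training already waits for the second term. Teachers learn their arm later and must hold the training dates until then. The schedule is tighter: the protocol wants several months of contact before perceptions are measured, and implementation runs from January, so T1, list closure and the draw must all fit before that start.

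**What it does not solve.** Student eligibility still requires all three questionnaires. That is a separate selection after randomisation, and this reordering leaves it in place.

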**Figure 1. Characteristics of the training program and timeline for data collection**

**Notes:** \*the variables assessed in PE teachers and students are detailed in the corresponding section; \*\*the

training program has two follow-up sessions (individual and group).

The study has been approved by the Ethics Committee of the University of [details masked for review process] and follows all ethical procedures established in the Declaration of Helsinki.

### **Sample size calculation**

The sample size for this intervention-based study was calculated using R Studio to ensure adequate power in the detection of potential statistically significant effects.

Considering a multi-level design nesting center, PE teacher and group, the sample size calculation was grounded on an anticipated effect size of 0.5, reflecting a moderate impact of the intervention. The power of the study was set at 80% with a significance level (alpha) of 0.05, aligning with common practices in educational research (McConnell et al., 2019).

Acknowledging the inherent structure of this study, an Intra-Class Correlation (ICC) of 0.1 was assumed based on similar educational settings (Hedges & Hedberg, 2007). This ICC estimate accounted for the expected homogeneity within the three levels (class group within PE teacher, PE teacher within center). To accommodate potential participant dropout, particularly among students, we incorporated a 40% anticipated dropout rate into our calculations (e.g., Meerits et al., 2022). The minimum sample size was adjusted to 210 students across 15 PE teachers, averaging 14 students per teacher. This adjustment ensures that our study maintains sufficient statistical power even in the face of anticipated losses, thereby safeguarding the integrity and validity of our findings.

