practical part (i.e., microteaching) has been previously identified as essential for applying what has been learned in contexts as close to reality as possible (Aelterman et al., 2013). Ultimately, the adoption of a congruent style, where trainers implement the program using (de)motivating teaching styles has also been positively perceived by PE teachers. This approach allows them to observe real-life examples of how to implement these strategies effectively (Aelterman et al., 2013). Moreover, in line with SDT, it could lead to an immediate effect on the teachers' need satisfaction during the training that has been positively associated with effectiveness and feasibility beliefs in terms of autonomy support and structure, as well as teachers' intentions to apply the proposed strategies (Aelterman et al., 2016).

Finally, while previous studies have considered gender as a covariate to analyze the effects of SDT-based interventions, gender differences in study variables are seldom reported for both teachers and students. Given prior SDT-related research indicating that (de)motivating teaching behaviours may be perceived differently by boys and girls students (White et al., 2021) and male and female teachers (García-Cazorla et al., 2024), it is crucial to determine whether the intervention is equally effective for both genders to mitigate any potential gender-related inequities.

To extend previous knowledge, this mixed-method study describes the protocol of a motivational training program, based on the circumplex model, aimed at improving (de)motivating teaching styles/approaches among PE teachers. The first hypothesis suggests that the features of the motivational training program will be positively perceived by PE teachers (H1). We also hypothesize that experimental school female and male teachers will perceive improvements in several antecedents, autonomy and competence satisfaction/frustration at work, (de)motivating teaching styles/approaches, and (mal)adaptive outcomes at least at the end of the intervention implementation toward students (H2). Finally,

both boys and girls from experimental groups will perceive improvements in their PE teachers' (de)motivating teaching styles/approaches, autonomy and competence satisfaction/frustration in PE, and adaptive outcomes in PE lessons (H3).

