### ***Analysis plan***

#### ***Quantitative analyses***

Firstly, the effects of the four sessions of the training program on the study variables assessed in teachers will be examined. The overall mean for each of the 11 variables perceived by PE teachers about the quality of the training program (e.g., interaction, innovation, interest, intelligibility, etc.) will also be calculated, representing the mean across the different sessions. A repeated measures analyses of variance (ANOVA) will be used to assess PE teachers' global appreciation of 11 variables related to the quality of the training program (e.g., interaction, innovation, interest, intelligibility, etc.) across the sessions of the training (i.e. within-subject analyses). Accordingly, each of the training sessions will be introduced as an independent variable (i.e. within-subject factor) and repeated measures of the PE teachers-related variables will be entered sequentially as dependent variables.

Secondly, the effects of the intervention implementation in PE lessons on study variables for both teachers and students will also be examined. Levene and Kolmogorov–Smirnov tests will be used to ensure the equality of variances and normal data distribution, respectively ( $p > .05$ ). Cronbach's coefficient will be calculated for each study variable across the three measurements. To examine the effects of the intervention on study variables, a  $3 \times 2$  (time x condition) repeated measures multivariate analysis of covariance (MANCOVA) will be performed for both teachers and students. Age, gender, teaching experience, type of school (public or private), and school location (rural or urban) will be introduced as covariates among teachers, while age, gender, and school grade level will be introduced as covariates among students. Subsequently, to examine intragender differences of the intervention on study variables, a  $3 \times 2 \times 2$  (time x condition x gender) repeated measures MANCOVA will be performed for both teachers and students. The same covariates will be entered as previously analysis, excluding gender. Multiple paired t-tests with Bonferroni correction will be calculated to determine between-group (i.e., experimental-control group) and within-group (i.e., pre-post) differences. Cohen's criteria will be used as indicators of small (.01), moderate

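### The 80% power is stated for the whole study but calculated for students only; at the same effect size, the teacher hypothesis (H2), tested on 16 to 20 teachers, has far less power on plausible assumptions

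*Protocol*

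**What the plan says.** The Sample size calculation section gives one power statement: "The power of the study was set at 80% with a significance level (alpha) of 0.05, aligning with common practices in educational research". On the effect, it says that "the sample size calculation was grounded on an anticipated effect size of 0.5". The other inputs are nesting by centre, teacher and class, an ICC of 0.1, and 40% dropout expected mainly among students. The result is 210 students across 15 teachers, 14 per teacher. The section ends by claiming sufficient power for the study, with no restriction to student outcomes.

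H2, stated at the end of the Introduction, concerns teachers: "experimental school female and male teachers will perceive improvements in several antecedents, autonomy and competence satisfaction/frustration at work", together with teaching styles and other teacher outcomes. H3 is the corresponding hypothesis for students. H1 concerns how the training is perceived.

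Under Quantitative analyses, a 3 x 2 (time x condition) "repeated measures multivariate analysis of covariance (MANCOVA) will be performed for both teachers and students". Participants and recruitment sets a minimum of 16 teachers, eight per arm, and adds: "The maximum number of participating teachers will be capped at 20". The protocol contains no teacher-level power calculation, and its Limitations section does not mention low power for teacher outcomes.

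**The concern.** Enrolling more students does not add information about a teacher's own job satisfaction, exhaustion or need satisfaction. The number of teachers limits power for H2, and that number is fixed between 16 and 20. The study-wide power statement therefore covers a main hypothesis that the calculation behind it does not address.

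H2 is one of the two effectiveness hypotheses, and the abstract itself notes that evidence on benefits for teachers is thinner than for students. A reader who takes the power statement at face value could treat a non-significant teacher result as a negative from an 80%-powered test. On plausible assumptions, that test would miss a true difference of 0.5 more often than it found it. A teacher effect that did reach significance would tend to be overestimated.

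**Working it through.** **1. The protocol's own figure.** Inputs: d = 0.5, alpha 0.05 (two-sided assumed, since the protocol does not say), power 80%, dropout 40%.
- Per arm: n = 2 x (1.960 + 0.842)^2 / 0.5^2 = 62.8, so 63 per arm and 126 in total.
- With dropout: 126 / 0.6 = 210, an exact match.
- The unit is the student, and the match holds only with the ICC left out. With 14 per teacher the design effect is 1 + 13 x 0.1 = 2.3, giving 126 x 2.3 = 290 completers and 290 / 0.6 = 483 enrolled.

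**2. Inputs for the teacher comparison.** 8 per arm (minimum) or 10 per arm (the cap, split equally); d = 0.5 carried over from the sample size section; two-sided alpha 0.05. Assumptions: one outcome, one value per teacher per time point, no teacher loss, no multiplicity correction, none of the five planned teacher covariates. The within-teacher correlation is not in the protocol, so a range is used.

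**3. Comparison at T3.** Noncentral t with noncentrality d x sqrt(n/2) and 2n - 2 degrees of freedom.
- 8 per arm: 0.5 x sqrt(4) = 1.00, 14 df, power 15%.
- 10 per arm: 0.5 x sqrt(5) = 1.12, 18 df, power 19%.
- Effect detectable with 80% power: d = 1.51 (8 per arm) or 1.32 (10 per arm).
- Teachers needed for 80% power at d = 0.5: 64 per arm.

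**4. Time x condition F test, one outcome.** Noncentrality = (n/2) x S / (1 - rho), where S is the sum of squared deviations of the T1, T2, T3 effects from their mean; 2 and 4n - 4 df; compound symmetry.

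| Effect at T1, T2, T3 | S | 8 per arm, rho 0.3 to 0.8 | 10 per arm, rho 0.3 to 0.8 |
|---|---|---|---|
| 0, 0.5, 0.5 | 0.167 | 12% to 32% | 14% to 40% |
| 0, 0.25, 0.5 | 0.125 | 10% to 25% | 12% to 31% |

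For example, with 10 per arm, rho = 0.8 and the first pattern: 5 x 0.167 / 0.2 = 4.17, power 40%.

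**5. T3 comparison adjusted for T1.** The effect becomes 0.5 / sqrt(1 - r^2), with one degree of freedom lost.

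| Assumed r | 8 per arm | 10 per arm |
|---|---|---|
| 0.5 | 19% | 23% |
| 0.7 | 25% | 31% |
| 0.8 | 34% | 42% |
| 0.9 | 56% | 68% |

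Power reaches 80% at r of about 0.94 (8 per arm) or 0.93 (10 per arm). At r = 0.7 the effect detectable with 80% power is d = 1.08 or 0.95.

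**The case against.** **It is a student calculation, not a wrong teacher calculation.** This stands. A reader might infer that the protocol computed power for H2 and got it wrong, or that it says in words that H2 has 80% power. It does neither. The fault is one of scope: a student calculation is presented as the power of the study. That is still an overstatement in the text, and not merely a detail left to a statistical analysis plan.

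**The effect of 0.5 may not be meant for teachers.** This is fair. Teachers receive the training directly and rate themselves, so a larger effect is possible. But the protocol gives no other effect size, and the detectable effects in the working do not depend on 0.5.

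**The design could reach 80%.** A reader might infer from the low figures that 80% is out of reach whatever the assumptions. The arithmetic does not support that: with T1 adjustment, a correlation of about 0.93 to 0.95 would suffice. Such a value would be optimistic, and the Quantitative analyses section does not list T1 as a covariate.

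**The planned test is multivariate, so one outcome is not a ceiling.** This is correct. For three uncorrelated outcomes, each with d = 0.5 (an assumption favourable to the plan), Hotelling's test gives 21% (8 per arm) or 27% (10 per arm) at T3, and about 51% or 66% with T1 adjustment at r = 0.8. These remain below 80%, but the single-outcome figures should not be called a best case.

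**One value per teacher is an assumption.** Teachers answer the teaching-style questionnaire with their selected groups in mind, which leaves open whether there is a response per class. Repeated responses from one teacher would not be independent, and the work-related scales are not tied to a class.

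**No section says that a null teacher result will be read as no effect, and focus groups supplement the teacher data.** True. The risk lies in what the power statement invites a reader to conclude.

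**Conclusion.** The point holds as one about the reach of the power statement. The 80% is claimed without restriction but rests on a calculation for students, and H2 is tested on 16 to 20 teachers. At the stated effect size, power for one teacher outcome is 15% to 19% for a T3 comparison, about 10% to 40% for the time x condition test (correlation 0.3 to 0.8), and 19% to 42% with T1 adjustment (correlation 0.5 to 0.8). At a correlation of 0.9 the T1-adjusted figure is still only 56% to 68%.

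These figures rest on assumed correlations, two-sided testing, a single outcome, and an effect of 0.5 that the protocol does not set separately for teachers.

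A reader might also infer that the 80% is sound once confined to students. It is not supported there either, because 210 reproduces only when the protocol's own ICC of 0.1 is ignored.

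**What to change.** Keep the number of teachers.

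1. In the Sample size calculation section, state that the calculation concerns student outcomes only. Recompute it with the ICC of 0.1 before repeating any 80% figure.
2. Add the teacher-level power or detectable effect, with the number of teachers and the assumed correlation beside it. For example: with 8 to 10 teachers per arm, power at d = 0.5 is about 15% to 19% for a T3 comparison, and 80% power needs d of about 1.5 to 1.3 (about 1.1 to 0.95 with T1 adjustment if the T1-T3 correlation is 0.7).
3. Remove the claim of sufficient power for the study as a whole.
4. In the analysis plan, report H2 as estimates with 95% confidence intervals, and state that a non-significant teacher result will not be read as absence of effect.

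For H2 the cost is a few sentences, with no extra teachers or measurements, and a less favourable stated power. Recomputing the student figure may raise the required number of students or lower the power that can be claimed for them.
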